8.4 Secondary Efficacy Evaluation

Observed means and mean changes from baseline for HbA1C and FPG will be analyzed by visit using a method similar to the primary endpoint.

Change from baseline to Week 12 (Visit 9, Part 2 Week 10) in PPG parameters during a MMTT, including AUC₀₋₆₀, AUC₀₋₁₂₀, and 1 & 2-hour PPG absolute levels and excursions will be analyzed using a method similar to the primary endpoint.

Changes from baseline to Week 12 (Visit 9, Part 2 Week 10) in mean 24-hour, mean day time (6 AM to 10 PM) and mean night time (10 PM to 6 AM) glucose as measured by CGM will be analyzed using a method similar to the primary endpoint. For a day to be included in the calculations of the overall means, the subject must have at least 80% of the expected glucose readings.

Changes from baseline to Week 12 (Visit 9, Part 2 Week 10) in weight will be analyzed using a method similar to the primary endpoint except that there will be no imputation for missing values (only observed values will be analyzed).

Proportion of subjects requiring glycemic rescue therapy during the treatment period will be summarized by frequency counts.

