	In the first two weeks of active treatment (Part 1) subjects will receive double-blind therapy according to their randomized regimen (ORMD-0801 8 mg or 16 mg, or excipient matched placebo) to be taken QHS or BID. Subjects will then enter Part 2 at the same dose and regimen administered in Part 1. Part 2:
	During Part 2, subjects will remain on fixed doses of ORMD-0801 (or placebo) for 10 weeks. Doses will not be adjusted unless clinically indicated for adverse events or hypoglycemia. Overall glycemia will be measured by A1C at baseline and over 12 weeks of treatment.
	Additional measures will include fasting plasma glucose (FPG) drawn at clinic visits, outpatient SMBG values and adverse events recorded in the diary. Subjects will undergo blinded continuous glucose monitoring (CGM) for 2 weeks at baseline (on at Visit 1, off at Visit 3) and end-of-study (on at Visit 8, off at Visit 9). Standardized Mixed Meal Tolerance Testing (MMTT) will be performed at baseline (Visit 3) and at end-of-study (Visit 9). A1C will also be measured at intervals.
	Throughout the 12-week treatment period, subjects will be monitored and may be considered for "rescue" in case of persistent symptomatic hyperglycemia (see Rescue Criteria) to restore adequate glycemic control.
Primary Endpoint	 Mean change in HbA1C from baseline to Week 12 (Visit 9, Part 2 Week 10) of the treatment period.
Secondary Endpoints	 Means and mean changes from baseline over time for HbA1C and FPG. Change from baseline to Week 12 (Visit 9, Part 2 Week 10) in postprandial glucose (PPG) parameters during a MMTT, including AUC₀₋₆₀, AUC₀₋₁₂₀, and 1 & 2-hour PPG absolute levels and excursions.
	 Changes from baseline in glycemic parameters measured using outpatient CGM. Change in weight from baseline to Week 12 (Visit 9, Part 2 Week 10) of the treatment period. Proportion of subjects requiring glycemic rescue therapy during
	 the treatment period. Safety assessed by adverse event reporting including adverse events of special significance such as hypoglycemia.
Exploratory Endpoints	Patient reported outcomes, by Diabetes Treatment Satisfaction Questionnaire _{status} (DTSQ _s) and Questionnaire _{change} (DTSQc) score over 12 weeks.
Duration of Participation	Subjects will be evaluated for participation in the study during a 1 to 3-week Screening period. Following Screening, eligible subjects will

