8.2 Sample Size

8.2.1 Cohort A

The primary efficacy endpoint is the change from baseline in HbA1C at Visit 9 (Part 2- Week 10) after 12 weeks of active treatment. Based on previous results, a drop in HbA1C of 0.6% is expected with a standard deviation of 1.2. The primary analysis is based on combining the BID and TID treatment regimens together to compare to combined placebo. In order to achieve 80% power, there 48 completers are needed per treatment group.

Assuming an approximate 20% drop out rate, 240 randomized subjects would yield around 192 completers or approximately 48 subjects per treatment group. This would provide 80% power to detect a decrease in HbA1C of 0.6% for the BID and TID active combined versus combined placebo.

An additional 20 non-randomized subjects will be enrolled to receive excipient matched placebo to ensure that the fish oil placebo does not have a significant effect on efficacy or safety. The choice of adding 20 subjects is not based on statistical considerations.

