8.3.2 Handling of Missing or Spurious Data

The overall data will be analyzed using a multiple imputation method to account for missing or spurious data. Missing or spurious data will be imputed. Imputed values are drawn for a distribution (that can be different for each missing entry). This step results in *m* complete data sets. Each of the *m* completed data sets will be analyzed. This step results in *m* analyses. The results for the *m* analyses will be pooled into a final result. The details of how the missing or spurious values were imputed will be documented.

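### Weight change to Week 12 is analysed on observed values only, leaving the Visit 5 and Visit 8 weights unused for subjects with no Week 12 weight: a modest loss of precision and a possible dropout bias

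*Combined protocol and SAP*

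**What the plan says.** The Synopsis lists as a secondary endpoint "Change in weight from baseline to Week 12 (Visit 9, Part 2 Week 10) of the treatment period". Section 8.4, repeated in the Synopsis under Statistical Methods, analyses it by a method similar to the primary one, except that "there will be no imputation for missing values (only observed values will be analyzed". No reason is given, and no sensitivity analysis is planned for weight.

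Section 8.3.2 sets the general rule: "The overall data will be analyzed using a multiple imputation method to account for missing or spurious data". It does not name the variables in the imputation model. The other continuous secondary endpoints in Section 8.4 carry no such exception; for the meal-test endpoints, for example, "1 & 2-hour PPG absolute levels and excursions will be analyzed using a method similar to the primary endpoint".

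Section 8.2.1 plans for substantial loss: "Assuming an approximate 20% drop out rate, 240 randomized subjects would yield around 192 completers or approximately 48 subjects per treatment group". Weight is measured at Visits 3, 5, 8, 9 and 10 and at any Rescue Visit (Sections 3.4 to 3.7 and Table 1). Under Section 3.8, a withdrawn subject returns the next day for the Visit 9 procedures, which include weight. The plan does not say whether that weight counts as a Week 12 value.

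**The concern.** Weight matters for an insulin product: Section 1 names weight gain as a drawback of injected insulin. A subject who leaves after Visit 5 or Visit 8 has already supplied information about the likely Week 12 weight. An analysis of observed Week 12 values ignores it.

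Two things follow. Precision is lost. The comparison also relies on dropout being unrelated to weight change once treatment and the baseline covariates are accounted for, because those covariates cannot correct for what happened on treatment.

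The protocol itself suggests one route by which weight could be linked to dropout. Section 3.7 lists weight loss among the symptoms of worsening hyperglycemia. Section 5.4 says that subjects who need more treatment but do not qualify for rescue will be considered for discontinuation. If the drug works, this could happen more often on placebo.

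**Working it through.** **1. The plan's own figure.** No sample size is stated for weight, so the HbA1C calculation serves only to fix the numbers per group. Section 8.2.1 gives "a drop in HbA1C of 0.6% is expected with a standard deviation of 1.2", 80% power, and BID plus TID combined (two groups) against one placebo group. Section 8.1 gives alpha 0.05; a two-sided test reproduces the stated number.

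n(placebo) = (1 + 1/2) × (1.960 + 0.842)² × (1.2/0.6)² = 1.5 × 7.85 × 4 = 47.1, or 48 with the t distribution (power 80.7%). Then 4 × 48 = 192 completers, and 192/0.8 = 240 randomized, or 60 per group. The plan's figures reproduce.

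**2. Loss against complete data.** If every dropout lacks a Week 12 weight, the SE rises by √(60/48) = 1.118, or 11.8%. Cohort B (15 enrolled, 12 completers per group, Section 8.2.2) gives the same: √(15/12) = 1.118. So does the 265 randomized to Cohort A in Section 5.2, where 0.8 × 265 = 212. Not all of this can be recovered.

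**3. The recoverable part.** Let d = 0.20 be the dropout share, q the share of dropouts with an interim weight, and r the correlation between interim and Week 12 weight change. The values of q and r are assumptions. The large-sample variance per arm, relative to complete data, is

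V = (1 − r²)/(1 − d) + r²/(1 − d + dq), against 1/(1 − d) = 1.25 for observed values only.

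- Low case, r = 0.5, q = 0.25: V = 0.75/0.80 + 0.25/0.85 = 1.2316. Effective n = 60/1.2316 = 48.7. SE ratio = √(1.25/1.2316) = 1.007.
- High case, r = 0.9, q = 1: V = 0.19/0.80 + 0.81/1 = 1.0475. Effective n = 57.3. SE ratio = 1.092.

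SE of the observed-values analysis divided by the SE using interim weights:

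| q | r = 0.5 | r = 0.7 | r = 0.9 |
|---|---|---|---|
| 0 | 1.000 | 1.000 | 1.000 |
| 0.25 | 1.007 | 1.015 | 1.025 |
| 0.5 | 1.014 | 1.028 | 1.048 |
| 1 | 1.026 | 1.053 | 1.092 |

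**4. Bias, by simulation.** The weight SD, correlations and dropout models below are all assumed.

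(a) Large samples, 20% dropout per arm, Visit 8 to Week 12 correlation 0.85. Dropout is random on placebo; on active it depends on Visit 8 weight change. Bias of the observed-values difference, in kg:

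| Odds ratio per SD of Visit 8 change | SD 2 kg | SD 3 kg | SD 4 kg |
|---|---|---|---|
| 1.0 | 0.01 | −0.01 | 0.00 |
| 0.7 | 0.12 | 0.18 | 0.23 |
| 0.5 | 0.23 | 0.31 | 0.43 |

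Using the Visit 8 weight, the bias is about 0.01 kg or less throughout.

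(b) 60 per arm, SD about 2.4 kg, true difference −0.8 kg, half of dropout after Visit 5 and half after Visit 8.
- Unrelated dropout: both analyses average −0.80, with SE 0.488 (observed only) against 0.458 (using Visits 5 and 8), a ratio of 1.066.
- Placebo gainers leave more often (log-odds slope 0.2 per kg): observed values give −0.69, off by 0.11 kg.
- The arms lose opposite tails (slopes 0.2 and −0.2): observed values give −0.56, off by 0.24 kg.
- Using Visits 5 and 8 gives −0.80 in all three settings.

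(c) As (b), but with dropout spread evenly over 12 weeks. Visits 5 and 8 fall at Weeks 2 and 10, so 2/12 of dropouts have no interim weight, 8/12 have Visit 5 only and 2/12 have both. Dropout before Visit 8 is taken as random. Assumed correlations with Week 12 are 0.8 to 0.9 for Visit 8 and 0.35 to 0.5 for Visit 5. The observed-values SE is about 2 to 4% larger. The two related-dropout settings give −0.74 to −0.77 and −0.72 to −0.74, so errors of 0.03 to 0.08 kg.

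**The case against.** The strongest defence is that weight is also a safety measure. It is listed under Safety Assessments (Section 6.1.1) and summarized with vital signs (Section 8.6.4), and Section 8.6.8 bars substitution of missing safety data. The exception agrees with that rule and is prespecified in two places. This may explain it, but a rule for descriptive safety summaries does not justify discarding information in a between-group comparison under Section 8.4.

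It is also fair that little rests on the result. Weight is one of several secondary endpoints in an exploratory Phase 2b study, with no power claim and no place in the testing sequence of Section 8.1. In the 60-per-arm simulations the bias is at most half a standard error (0.24 against 0.49). That stands, and it sets the priority.

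The near-zero bias with interim weights in (a) and (b) follows from letting dropout depend only on weights already observed. No weight is scheduled between Weeks 2 and 10, so if dropout in that interval tracks weight, a Week 2 value will not fully correct for it. That also stands.

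A reader might infer three stronger points that the documents do not support:

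- *The analysis is restricted to completers.* The text says observed values. Rescued subjects stay in the study (Section 3.7), and withdrawn subjects should have a weight taken (Section 3.8). What is unclear is how that last weight is used.
- *Weight rests on a stronger assumption than every other endpoint.* Section 8.3.2 does not name its imputation variables. Imputing from baseline covariates alone would rest on the same assumption as the observed-values analysis and gain nothing. That the other secondary endpoints are imputed at all is a fair reading of a method similar to the primary, but it is not stated.
- *The weight result will be biased.* It will not be if missingness depends only on treatment and the model covariates.

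**Conclusion.** The point holds as a minor one. For subjects without a Week 12 weight, the planned analysis leaves interim weights unused. The SE is roughly 1 to 9% larger than necessary for assumed correlations of 0.5 to 0.9 and a quarter to all of dropouts having an interim weight. It is about 2 to 4% larger if dropout is spread evenly, and no larger if dropouts have no interim weight. Bias is a risk and not a certainty: about 0.03 to 0.4 kg under the assumed SDs (2 to 4 kg) and dropout models, in a direction that depends on who leaves, and none if dropout is unrelated to weight. The plan supplies only the 20% dropout and the visit schedule; the other inputs are assumptions. If early-withdrawal weights were counted as Week 12 values, fewer subjects would be lost, but weights from different times would be mixed. The primary HbA1C conclusion is unaffected.

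**What to change.** Delete the exception in Section 8.4 and the Synopsis. Analyse weight with a mixed model for repeated measures on Visits 5, 8 and 9, adjusted for baseline weight. Alternatively, use multiple imputation whose model includes baseline, Visit 5 and Visit 8 weight. State that the early-withdrawal weight (Section 3.8) enters at the time it was measured and is not treated as a Week 12 value. Keep the observed-values analysis as a sensitivity analysis.

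The cost is wording and slightly more analysis work; no new data, visits or subjects are needed. The analysis would rest on a missing-at-random assumption that the interim weights may not fully satisfy, which is one reason to report both results. The change should be made before unblinding.

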8.5 Exploratory Efficacy Evaluation

Patient reported outcomes, by Diabetes Treatment Satisfaction Questionnaire_{status} (DTSQ_s) and Questionnaire_{change} (DTSQc) score over 12 weeks will be evaluated.

Excipient matched placebo will be compared to the fish oil placebo on the following endpoints:

- Change in HbA1c from baseline to Week 12
- Frequency of adverse events
- Frequency of hypoglycemic events.

8.6 Safety Evaluation

8.6.1 Safety Population

All randomized subjects who receive at least one dose of study treatment will be included in the safety analysis population.

8.6.1.1 Safety Evaluation Part 1

Adverse events will be described as "Part 1 Emergent," defined as any AE that started (or worsened) after receiving the first dose of randomized treatment during Part 1 until the time of receiving the first dose of randomized treatment during Part 2 (or discontinuation from Part 1).

8.6.1.2 Safety Evaluation Part 2

Adverse events will be described as "Part 2 Emergent," defined as any AE that started (or worsened) after receiving the first dose of randomized treatment during Part 2.

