In the event that a subject discontinues the study prior to completion, the date the subject is withdrawn and the reason for discontinuation will be recorded in the source documents and eCRF. Although a subject will not be obliged to give his/her reason for withdrawing prematurely, the investigator will make a reasonable effort to obtain the reason while fully respecting the subject's rights.

All subjects who are randomized and treated (i.e., received any amount of study treatment) will be included in the safety analyses. Thus, every effort will be made to contact any subject who fails to attend any follow-up appointments/contacts, in order to ensure that he/she is in satisfactory health. If a subject withdraws from the study as a result of meeting discontinuation criteria (Section 4.3) after the start of study treatment administration, reasonable efforts should be made to have the subject return for the early withdrawal evaluations (Section 3.8). Any subject withdrawn due to a

suspected study treatment -related AE should be followed until resolution or stabilization of the event.

If a subject becomes pregnant, study treatment will be discontinued immediately. The subject will be followed until delivery or other termination of pregnancy for outcome.

The Sponsor has the right to terminate this study, and the Investigator/Investigational Site has the right to close the site, at any time, although this should occur only after consultation between involved parties. The Investigator will notify the IRB in writing of a premature termination of a study or closure of Investigational Site, and will send a copy of the notification to the Sponsor.

Events that may trigger premature termination of a study or closure of an Investigational Site include, but are not limited to, a new toxicity finding, a request to discontinue the trial from a regulatory authority, non-compliance with the protocol, GCP violations, slow recruitment/low enrollment, or change in development plans for the study treatment.

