5.2 Randomization

Of the total 360 subjects, 265 subjects will be randomized to Cohort A and receive ORMD-0801 or placebo in one of 3 treatment regimens: QHS, BID, or TID. The actual treatment (ORMD-0801 or placebo) will be double-blinded to the subjects, investigators, monitors, and staff members responsible for treating and evaluating subjects, but the treatment regimen will be unblinded.

Creation, maintenance, and communication of the randomization scheme will be managed by an interactive web-based response system (IWRS). Subjects will be randomized 1:1:1 to QHS, BID, or TID and 1:3 (placebo:ORMD-0801) within each of those regimens at Visit 3. Therefore the overall randomization will be 1:1:1:1 (all placebo dosing regimens combined: ORMD-0801 QHS: ORMD-0801 BID: ORMD-0801 TID). Randomization will be in block sizes of 12 (1:3;1:3;1:3 [placebo QHS: ORMD-0801 QHS; placebo BID: ORMD-0801 BID; placebo TID: ORMD-0801 TID]).

An additional 75 subjects will be randomized to Cohort B and receive one of 5 treatment regimens (1:1:1:1): excipient matched placebo QHS, ORMD-0801 8 mg QHS, ORMD-0801 8 mg BID, ORMD-0801 16 mg QHS, or ORMD-0801 16 mg BID. Randomization will be in block sizes of 5 (1:1:1:1:1 [excipient matched placebo QHS: ORMD-0801 8 mg QHS: ORMD-0801 8 mg BID: ORMD-0801 16 mg QHS: ORMD-0801 16 mg BID]).

The randomization will be centralized and stratified by a) Sulfonylurea usage and b) whether they are on metformin alone or metformin plus one or 2 additional oral antidiabetic drugs at Screening. This will help ensure balanced treatment distribution of the subjects across the strata.

The additional 20 subjects in Cohort A who will receive excipient-matched placebo will not be randomized.

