7.2 Definition of Adverse Event

An adverse event (AE) is defined in 21 CFR 312.32(a) as follows:

Any untoward medical occurrence associated with the use of a drug in humans, whether or not considered drug related.

An AE can be any unfavorable and unintended sign (e.g., an abnormal laboratory finding), symptom, or disease during the course of the study, and does not imply any judgment about causality.

Treatment-emergent adverse events (TEAEs) are defined as any AE that starts or increases in severity after the first randomized dose of study treatment (active or placebo).

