8.6.2 Adverse Events

AEs will be coded using the most current version of MedDRA. The severity of AEs will be graded according to NCI CTCAE version 4.03.

The incidence of TEAEs will be tabulated by MedDRA preferred term, system organ class, treatment group, severity, and assigned relationship to study treatment. The incidence for each TEAE will be provided as the total number of subjects that experienced the TEAE, as well as the percentage of the population that this represents. If a TEAE is reported more than once for a given subject, the greatest severity and the worst-case attribution will be presented in the summary tables.

TEAEs will be listed for individual subjects, along with information regarding onset and end dates, onset time where available, severity, seriousness, relationship to study treatment, action taken, and outcome. A similar listing will be prepared for the pretreatment AEs.

Pretreatment AEs and TEAEs that lead to withdrawal from the study will be separately listed and summarized. Similarly, separate tabulations and listings will be prepared for pretreatment and treatment-emergent SAEs.

Descriptive statistics will be generated as appropriate (i.e., frequency for categorical data). Inferential statistical analysis comparing the AE data between active and placebo is not planned.

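### As worded, the safety population and treatment-emergent AE definitions leave out the 20 non-randomized TID excipient-placebo subjects, who were added partly as a safety check

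*Combined protocol and SAP*

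**What the plan says.** Two places define who enters the safety analyses, and both require randomization. Section 8.6.1: "All randomized subjects who receive at least one dose of study treatment will be included in the safety analysis population". Section 4.3: "All subjects who are randomized and treated (i.e., received any amount of study treatment) will be included in the safety analyses".

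Three places define when an event counts as emergent, and all three start from randomized dosing. In Section 7.2 a TEAE is an event that "starts or increases in severity after the first randomized dose of study treatment (active or placebo"). In Section 8.6.1.1, Part 1 emergence begins "after receiving the first dose of randomized treatment during Part 1". In Section 8.6.1.2, Part 2 emergence is "defined as any AE that started (or worsened) after receiving the first dose of randomized treatment during Part 2".

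Section 8.6.2 builds its tables on these terms: "The incidence of TEAEs will be tabulated by MedDRA preferred term, system organ class, treatment group, severity, and assigned relationship to study treatment". For serious events, "separate tabulations and listings will be prepared for pretreatment and treatment-emergent SAEs"; AEs leading to withdrawal are split the same way.

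Section 5.2 then says: "The additional 20 subjects in Cohort A who will receive excipient-matched placebo will not be randomized". Section 3.1 adds that the group was requested by FDA, is single-blind and is dosed TID. Section 8.2.1 gives its purpose: to check that the fish-oil placebo has no material influence on efficacy or safety.

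**The concern.** The group was added to answer a question that is partly about safety, yet the safety definitions turn on a condition that the group is designed not to meet. A programmer who follows Sections 7.2 and 8.6.1 exactly would build a safety population and a set of TEAE tables without these 20 subjects.

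Section 8.6.2 adds a second gap. It gives SAEs and AE withdrawals only two classes, pretreatment and treatment-emergent. An on-treatment SAE in one of the 20 is not pretreatment in any ordinary sense and, as worded, is not treatment-emergent either. It has no on-treatment table to enter.

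At stake is the tabulated safety record of the only subjects who take excipient placebo three times a day. If the question is first met at programming, the decision on whether FDA-requested safety data are tabulated could be made after results are known.

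**Working it through.** **Inputs**
- Planned total: about 360 (Synopsis; Section 3.1).
- Randomized in Cohort A: 265 (Section 5.2).
- Non-randomized excipient placebo, TID: 20 (Sections 3.1 and 5.2).
- Randomized in Cohort B: 75, in five groups of 15, one of which is excipient placebo QHS (Sections 5.2 and 8.2.2).

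**The plan's total.** 265 + 20 + 75 = 360. This matches the stated figure, so the 20 are counted as study subjects.

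**Safety population as written, if everyone is dosed.** 265 + 75 = 340. The shortfall is 360 − 340 = 20, and 20/360 = 5.6%. Within Cohort A, 20/(265 + 20) = 20/285 = 7.0%.

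**Excipient-placebo subjects**

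| | As written | If defined by treatment-period dosing |
|---|---|---|
| Cohort B, QHS | 15 | 15 |
| Cohort A, TID | 0 | 20 |
| Total | 15 | 35 |

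The 20 are 20/35 = 57% of all excipient-placebo subjects and 100% of those dosed TID. The 15 in Cohort B take one dose a day, not three, so they do not replace the missing group.

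**What the 20 contribute.** If no case of a given AE is seen among n subjects, the one-sided 95% upper bound on its rate is 1 − 0.05^(1/n).
- n = 15 (Cohort B alone): 1 − 0.05^(1/15) = 18.1%
- n = 20 (the TID group alone): 1 − 0.05^(1/20) = 13.9%
- n = 35 (both, if pooling were accepted): 1 − 0.05^(1/35) = 8.2%

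The chance of seeing at least one case is 1 − (1 − p)^n. The documents give no AE rate, so p is assumed.

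| Assumed rate p | n = 15 | n = 20 | n = 35 |
|---|---|---|---|
| 2% | 26% | 33% | 51% |
| 5% | 54% | 64% | 83% |
| 10% | 79% | 88% | 97% |

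These figures show how much information the group carries. They do not measure bias in any planned result.

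**Whether another section brings the 20 back in**
- Section 8.5 compares excipient with fish-oil placebo on HbA1C change, AEs and hypoglycemia. It names no analysis set and no emergence rule, and it could be carried out on the 15 Cohort B subjects alone. Inclusion of the 20 is unspecified, not ruled out.
- Section 8.6.8 promises descriptive statistics and listings for all data. It supplies neither a TEAE denominator nor an on-treatment class for these subjects.
- Section 8 leaves further detail to a statistical analysis plan. That can add to the stated definitions but does not reverse them.
- No passage makes an exception for the 20.

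**The case against.** The best counter-argument is that *randomized* is loose shorthand for *after the run-in*. AE monitoring begins during the placebo run-in (Section 7.5), so the definitions need some term to separate run-in from treatment. The protocol is loose in the same way elsewhere: Section 5.3.1.2 says that all subjects receive double-blind treatment under a randomization schedule, and footnote 4 to Table 1 is similar. Neither is literally true of the 20. This may well explain the phrase about the first randomized dose. It does not explain Sections 4.3 and 8.6.1, where the word describes the subject and not the dose.

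A second argument is that those two sentences say who is included and never say *only*, and that the one in Section 4.3 mainly supports follow-up contact. That is true of the grammar, but a population definition is ordinarily read as complete.

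A third is that Section 8.5 already delivers the safety check, and that it speaks of adverse events in general rather than TEAEs. This has force: it means the 20 are not shut out of that comparison. But the section does not place them in it either.

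The points on impact stand. AEs and hypoglycemic events in the 20 are recorded (Sections 7.5 and 7.3.1), SAEs are reported within 24 hours (Section 7.5.2), and the trial-stopping criteria in Section 4.3 do not depend on randomization. It is also reasonable to keep a non-randomized, single-blind group out of the randomized comparisons; a separate column does that.

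**Conclusion.** The concern holds. Applied as written, the definitions give a safety population of at most 340 of the 360 planned subjects and put no TID excipient-placebo data in the TEAE, SAE or AE-withdrawal tables, contrary to the purpose in Section 8.2.1. A stated rule gives the wrong analysis set, so this is more than missing detail. The exception is the pooling question in Section 8.5, which is only unspecified.

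The impact is limited. The primary analysis, the HbA1C comparison in Section 8.5 and the randomized active-versus-placebo safety tables are unaffected, and no event goes uncollected. It should be corrected before database lock.

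The conclusion assumes that *randomized* carries its plain meaning and that the definition in Section 8.6.1 is exhaustive. The count of 340 also assumes that every planned subject is enrolled and dosed.

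**What to change.** 1. In Sections 4.3 and 8.6.1, define the safety population as all subjects, randomized or assigned, who take at least one dose of treatment-period study medication from Visit 3.
2. In Section 7.2, start TEAE emergence at the first treatment-period dose. In Sections 8.6.1.1 and 8.6.1.2, start it at the first treatment-period dose of the part concerned. The run-in placebo is still excluded.
3. In the TEAE, SAE and AE-withdrawal tables, show the 20 in a separate column labelled non-randomized, so that the randomized comparisons stay as they are.
4. In Section 8.5, name this set for the AE and hypoglycemia comparison, and state whether the 15 Cohort B excipient-placebo subjects are pooled with the 20 or shown apart.

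The cost is wording in those sections and one column in the AE tables. No new data, visits or subjects are needed.
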